Aim 1: Document the impact of DPP-BI compared to DPP-MS on weight at 12, 18, and 24 months.

Hypothesis 1: Overall, DPP-BI compared to DPP-MS will result in more favorable weight loss (average change and the proportion reaching $\geq 5\%$) at 12, 18, and 24 months.

Aim 2: Document the impact of DPP-BI compared to DPP-MS on cardiometabolic, physical activity/function, secondary outcomes, and behavioral adherence measures at 12, 18 and 24 months.

Hypothesis 2: Overall, DPP-BI compared to DPP-MS will result in more favorable cardiometabolic, physical activity/function, secondary outcomes, and behavioral adherence measures at 12, 18, and 24 months.

Reducing cardiometabolic risk and promoting functional health in community-based elders with obesity and pre-diabetes: evaluating sustainable follow-up strategies

Exploratory Aim: We will examine differences in intervention response (weight, cardiometabolic, and function) by race (African American, Caucasian). For a proportion of the sample, we will explore Medicare data for group differences in medical utilization (medications, outpatient, inpatient, emergency visits) and participation in activity programs.

Evaluating incremental refinements to standard DPP approaches through community centers providing aging services, in alignment with MDPP^{1,37} and other Medicare subsidized activity benefits, will improve our understanding of the most effective and potentially sustainable long term approaches for weight control and health maintenance in vulnerable older adults. A successful demonstration of 12-, 18- and 24-month interventions using video- and telephone-coaching strategies to sustain weight loss self-management and enhance behavioral activation for cardiometabolic control and functional health outcomes would have significant individual and public health benefit.

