4.0 Study Endpoints

The Sustain study primary endpoint is 24-months, and important secondary endpoints are examined at 18, 12, and 6-months. All study endpoints are indexed from baseline assessment; however, randomization does not occur until the six-month assessment.

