18.0 Data Analysis Plan

All analyses are conducted in consultation with the study biostatisticians, using SAS 9.4 (SAS Institute, Inc., Cary NC). Descriptive analyses and graphic displays are used to identify outliers, missing data, and patterns of attrition. Demographic variables and baseline measures are contrasted between the Active Comparator: DPP-Behaviorally Intensive 30-Minute Groups (DPP-BI) and the Placebo Comparator: DPP Minimal 15-minute Calls (DPP-MIN) conditions. In all outcome analyses we will use an intent-to-treat (ITT) approach in which participants remain in the study arm to which they are randomized regardless of attrition. The primary analytic strategy is a linear or generalized mixed-effect models approach in which treatment group, time, and time by group interaction are treated as fixed effects, and subject is treated as a random effect to account for individual subject variability. Hypothesis tests are two-sided, and significance will be set at the 0.05 level. Mixed models are applicable to longitudinal datasets that contain missing observations, with the assumption that the data are missing at random. Our prior intervention studies suggest that we can anticipate 90% retention at 6 months and greater than 80% retention over the 18-month extended intervention period (at 24 months) with no differential attrition between arms. Those who drop out or are lost to follow-up are compared to those who have completed intervention for research assessments using standard parametric and non-parametric methods, as appropriate. We will examine the patterns of missingness and, if necessary, account for missingness in outcome analysis (e.g., the covariate approach). Regression modeling will be conducted to adjust for covariates such as race, sex, age, socio-demographic factors, and other designated baseline clinical variables.

Research Questions

Reducing cardiometabolic risk and promoting functional health in community-based elders with obesity and pre-diabetes: evaluating sustainable follow-up strategies

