Analysis Plan for Hypotheses 1 and 2: We will apply mixed effect models to evaluate differential changes in weight measures at 6, 12, 18, and 24 months from baseline, with fixed terms of group (DPP-BI vs. DPP-Min), time as a factor (6,12,18, and 24 months), and the group by time interaction. We employed the following steps as the pre-randomization balancing logic: (1) group subjects by weight loss status (≤ 3.5 vs. > 3.5 percent at 6-months) and age (≤ 70 vs. > 70 years at baseline), (2) group subjects by sex (male vs. female) and race (Black/African American or Black/Mixed/Other vs. White/Caucasian), (3) group subjects using all 4 factors (based on 2x2 frequency table) and (4) randomly assign the subjects in the same cell into 2 conditions (DPP Plus vs. DPP Minimal). Subject was included as a random term. To test the differential treatment effect, evaluated the coefficients that are associated with the group and the group by time interaction by using an F test. Planned contrasts will be set up from the mixed models to compare the improvement in weight from baseline to Months 12, 18 and 24 between the two conditions (DPP-BI vs. DPP-Min). In addition, a generalized mixed-effect model was fit to the binary outcome of achieving $\geq 5\%$ weight loss at 6, 12, 18, and 24 months, with the logit link, which includes similar fixed and random terms as above. Average percent weight loss and the proportions achieving $\geq 5\%$ weight loss are compared between the two groups at 12, 18 and 24 months. Similar analyses were performed for fasting glucose, HbA1c, and insulin (and other biometric measures), physical activity/function, and other secondary outcomes at subsequent assessment points.

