The planned contrasts were set up to compare differential changes from baseline to Months 12, 18, and 24. Benjamini-Hochberg's method was used to control for the overall type I error for multiple secondary outcomes. More intensive modeling is performed to account for factors that are known to affect the outcomes as well as those that have been found to differ between treatment conditions at baseline and at Month 6 (the timepoint at which participants are stratified by $<$ or $\geq 3.5\%$ weight loss and other factors and randomly assigned to the two 18-month conditions). We also perform analyses in which we restrict our linear and generalized mixed-effect analyses to those who did not reach $\geq 5\%$ weight loss at 6 months and set up the contrasts to compare DPP-BI with DPP-MIN, on average, and the proportion reaching $\geq 5\%$ at 12 months and 18 months from baseline.

Exploratory Aim. We examine available Medicare data for those insured by a large regional payer to assess group and time from baseline differences in medical utilization metrics (e.g., type of outpatient, inpatient, or emergency visits) and participation in activity programs, for a proportion of the sample. We will extract Medicare data on numbers of outpatient, inpatient and emergency visits, and number of subjects participating in activity programs, and compare the numbers between the two conditions using linear and generalized regression models. We will explore the potential moderation effects of sex and race. We will include the interaction of sex by group or race by group in the mixed-effect models, as well as the three-way interaction of sex, group and time or race, group and time, if the group by time interaction is significant in the original model.

Reducing cardiometabolic risk and promoting functional health in community-based elders with obesity and pre-diabetes: evaluating sustainable follow-up strategies

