mixed-effect analyses to those who did not reach $\geq 5\%$ weight loss at 6 months and set up the contrasts to compare DPP Plus with DPP Minimal, on average, and the proportion reaching $\geq 5\%$ at 12 months and 18 months from baseline.

Exploratory Aim: Examine available Medicare data for those insured by a large regional payer to assess group and time from baseline differences in medical utilization metrics (e.g., type of outpatient, inpatient, or emergency visits) and participation in activity programs, for a proportion of the sample. We will extract Medicare data on numbers of outpatient, inpatient and emergency visits, and number of subjects participating in activity programs, and compare the numbers between the two conditions using linear and generalized regression models. We will explore the potential moderation effects of sex and race. We will include the interaction of sex by group or race by group in the aforementioned mixed-effect models, as well as the three-way interaction of sex, group and time or race, group and time, if the group by time interaction is significant in the original model.

Power and Sample Size Considerations. We powered this study on the main comparisons between the Active Comparator: DPP Plus 30-minute Calls (DPP Plus) and the Placebo Comparator: DPP Minimal 15-minute Calls (DPP Minimal) on average weight loss at 12 months from baseline. With 180 subjects per arm and projected 90% attritions at Months 12, we would have 80% power to detect effect sizes of 0.31, using two-sided t tests at the 0.05 level. Our prior Pitt Retiree study observed approximately 7.5 % weight reduction at 12 months among those subjects who received active intervention for 12 months, and 5.5% reduction at 12 months among those in the placebo comparator group. Assuming similar effects and similar standard deviation of 5.8% as observed in the Pitt Retiree study, we expect to see a standardized group difference ranging 0.34 at Months 12 between DPP Plus and DPP Minimal. We anticipate that our projected sample size will enable us to detect group differences with power greater than 0.8 for our primary weight outcome.

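### The race (or sex) × group × time term, the direct test of moderation, is fitted only if the overall group × time interaction is significant, although the aim on race is unconditional

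*Protocol*

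**What the plan says.** Protocol 2.0 (Objectives, Exploratory Aim) states the aim without any condition: "We will examine differences in intervention response (weight, cardiometabolic, and function) by race (African American, Caucasian"). Sex is not named there.

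Protocol 18.0 (Data Analysis Plan, Exploratory Aim) adds sex and describes the models. The two-way terms come first: "We will include the interaction of sex by group or race by group in the mixed-effect models". The three-way terms with time follow, subject to "if the group by time interaction is significant in the original model". The SAP's Exploratory Aim paragraph has the same rule: "as well as the three-way interaction of sex, group and time or race, group and time, if the group by time interaction is significant".

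Two other statements determine what the rule does. Protocol 4.0 says that "randomization does not occur until the six-month assessment". The model in Protocol 18.0 has "time as a factor (6,12,18, and 24 months), and the group by time interaction".

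Neither document says what will be reported on race if the overall interaction is not significant.

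**The concern.** The aim asks whether the effect differs by race. The condition tests something else: whether the average arm difference changes over time. A trial can fail the second test while the answer to the first is yes.

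The design makes this matter. Any arm difference at Month 6 arose before assignment, so its expected value is zero. The treatment effect therefore appears as a change in the arm difference from Month 6 to later visits, which is the group × time interaction. A difference in that effect between races appears in race × group × time, which is the conditional term. The two-way race × group term averages the arm difference over four visits, one of which carries no effect.

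At stake is whether a trial that aims for 25% minority enrollment, and balances its randomization on race, is sure to report arm differences by race at 24 months, its primary endpoint. The aim also covers cardiometabolic and functional response. The documents state power only for weight, so for those outcomes the chance of meeting the condition is unknown.

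**Working it through.** **Inputs from the documents.** 180 per arm; standardized effect 0.31 detectable with 80% power at Month 12; expected effect 0.34 (2.0/5.8 = 0.345); two-sided 0.05; minority share 25%; retention above 80% at Month 24.

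**Assumptions not in the documents.** The subgroup effects; compound symmetry with between-visit correlation ρ of 0.5, 0.7 or 0.8; an effect of zero at Month 6 and constant at Months 12, 18 and 24; the 25% share taken as the smaller race subgroup.

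**The plan's own figure.** The text says 90% attrition at Month 12, but only 90% retention (162 per arm) reproduces the result: (1.960 + 0.842) × √(2/162) = 0.311, and power at 0.31 is 79.4%. Read literally, 18 per arm would give about 15%. I use 162. No power is stated for moderation.

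**Formulas.** Let n be the number per arm, p = 0.25 the subgroup share, d̄ the average effect and δ the difference in effect between subgroups. For the effect pattern (0, d, d, d):

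- Overall group × time, 3 df: λ = (n/2) × d̄² × 0.75/(1 − ρ).
- Three-way term, 3 df: λ = (n/2) × δ² × 0.75/(1 − ρ) ÷ k, with k = 1/0.25 + 1/0.75 = 5.333.
- Two-way term: expected value 0.75δ, variance (1 + 3ρ)/4 × (2/n) × k.

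**Example.** For effects +0.34 (White) and −0.34 (minority), d̄ = 0.75 × 0.34 − 0.25 × 0.34 = 0.17 and δ = 0.68. At ρ = 0.5, the overall λ is 81 × 0.0289 × 1.5 = 3.51 (power 32%), and the three-way λ is 81 × 0.4624 × 1.5/5.333 = 10.53 (power 78%).

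**Results, 162 per arm, for ρ = 0.5 / 0.7 / 0.8:**

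| Effect, White / minority | d̄ | Condition met | Three-way power | Two-way power |
|---|---|---|---|---|
| 0.34 / 0.34 | 0.34 | 90 / 99 / >99% | – | – |
| 0.34 / 0 | 0.255 | 65 / 87 / 97% | 24 / 39 / 56% | 24 / 20 / 19% |
| 0.34 / −0.34 | 0.17 | 32 / 51 / 70% | 78 / 95 / 99.5% | 71 / 62 / 58% |
| 0 / 0.34 | 0.085 | 11 / 15 / 21% | 24 / 39 / 56% | 24 / 20 / 19% |

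With the unrounded 2.0/5.8 in place of 0.34, the second row becomes 66–98% for the condition and 25–57% for the three-way test.

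**Combined effect in the third row.** The overall estimate and the subgroup contrast are uncorrelated under these assumptions, so the chance that the three-way test is both run and significant is about the product: 0.316 × 0.783 = 25%, 0.505 × 0.954 = 48%, 0.697 × 0.995 = 69%. Without the condition it is 78%, 95% and 99.5%.

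**At 80% retention (144 per arm), third row.** The overall λ runs from 3.12 to 7.80, so the condition is met in 28–64% of trials. The three-way λ runs from 9.36 to 23.41, for power of 73–99%.

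**The case against.** The strongest reply is that asking for an overall signal before fitting higher-order interactions is a recognised restraint on exploratory testing, and these models recur across many outcomes. That is fair as a rule about claims. It is not a reason to leave estimates and intervals out of the plan.

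A reader might infer that the exploratory aim goes unanswered when the condition fails. The documents do not support that. On the natural reading the condition attaches only to the three-way term, so a race × group estimate is produced either way, with 58–71% power for opposite effects. The Medicare part of the aim is unconditional: the plan will "compare the numbers between the two conditions using linear and generalized regression models". Moderation by sex is not part of the aim as stated in Protocol 2.0.

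A reader might also infer that heterogeneity always closes the door. It does so only when it lowers the average. Effects of 1.5 points in White and 3.5 in minority participants average 0.75 × 1.5 + 0.25 × 3.5 = 2.0 points, and the condition is then as likely to be met as with a uniform 2.0.

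A third inference is that the condition biases the moderation result upward. Because the contrast is uncorrelated with the overall estimate, selection on the overall test leaves it essentially unbiased. The subgroup-specific effects are inflated. In a single-visit approximation with true effects of 2.0 and 0 points and 144 per arm, the standard error is 5.8 × √(2/144) = 0.68 and the expected z is 1.5/0.68 = 2.2. Selection on significance then adds about 0.45 points to each subgroup estimate.

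It also stands that opposite effects by race have no support in the documents, and that for 0.34 / 0 the moderation test is weak with or without the condition.

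**Conclusion.** The point holds as a minor one. Both documents make the direct test of moderation depend on a different hypothesis, the aim on race has no such condition, and no fallback is stated. The unconditional two-way term gives only an attenuated answer because it includes the pre-randomization visit.

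The size depends on the pattern of effects. With opposite effects of 0.34 in a 25% subgroup, the condition is met in about 32–70% of trials although the test it controls has 78–99.5% power. With benefit only in the minority subgroup it is met in about 11–21%. With benefit only in White participants it is usually met (about 65–97%), and power of about 24–56% for moderation is then the main limit. These ranges rest on the assumed subgroup effects, compound symmetry and correlations of 0.5 to 0.8, none of which the documents give. Hypotheses 1 and 2 are not touched.

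**What to change.** In Protocol 18.0 and the SAP, delete the condition on the three-way term. State that race × group × time (and sex × group × time, if sex is kept) is fitted whatever the overall test shows. For each subgroup, always report the arm difference at Months 12, 18 and 24 with a 95% confidence interval, together with the interaction contrast, labelled exploratory. If the two-way terms are retained, say that they are unconditional and that they average over Month 6. If sex is kept, name it in the aim in Protocol 2.0.

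The cost is one deleted clause and one small table per outcome. No new data are needed and the primary analysis does not change. The downside is a few more exploratory estimates, with wide intervals in the smaller subgroup, to be read with caution.

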19.0 Provisions to Monitor the Data to Ensure the Safety of Subjects

In this minimal risk Sustain study, we utilized a Data and Safety Monitoring Plan (DSMP) to ensure the safety of study participants and the validity and integrity of data in compliance with NIH/NIDDK and our local IRB. The DSMP was reviewed annually by a single data safety monitoring officer via written report and teleconference.

An AE is defined as any untoward medical or psychological event experienced by a subject during or as a result of his/her participation in the study that represents a new symptom or an exacerbation of an existing condition whether or not considered study-related based on appropriate medical judgment.

SAEs are any adverse experience that results in any of the following outcomes:

- Death
- Imminently life-threatening event/illness
- Inpatient hospitalization or prolongation of existing hospitalization
- Persistent or significant disability/incapacity
- Pregnancy resulting in a congenital anomaly/birth defect
- Any event requiring medical or surgical intervention to prevent permanent impairment or damage. In this study, this is defined as physician confirmed diagnosis of any of the following: angina pectoris, heart attack, stroke, transient ischemic attack, heart failure, coronary angioplasty or bypass surgery, peripheral vascular disease, incident diabetes, serious musculoskeletal injuries (e.g., fractures, ruptured ligaments), liver failure, kidney failure, and cancer (except for non-melanoma skin cancer).

Non-SAEs are all adverse events that do not meet the above criteria for “serious.”

Blinded Reporting. Safety information for this study is reported to the Safety Officer by masked treatment group (i.e., without revealing the treatment assignment of each group). With each report, summaries of the numbers and rates of all AEs by masked treatment group are provided.

Reducing cardiometabolic risk and promoting functional health in community-based elders with obesity and pre-diabetes: evaluating sustainable follow-up strategies

Expedited reporting. All unexpected SAEs must be reported to the safety officer within 5 business days of discovery, regardless of any judgment of their relatedness to the study treatment. The safety officer may require a conference call to review relevant information (and the site study physician's determination of whether there was any possible relevance to the study) and discuss and approve the investigators' Corrective and Preventive Action Plan, if warranted.

Data quality monitoring. The safety officer receives an annual report on data quality and completeness. At a minimum, this report will include the following: (1) participant accrual and follow-up completion/retention by site in relation to goals and timeline; (2) the randomization process and group comparability on the balancing variables; (3) data completeness for primary and secondary outcome measures; and (4) protocol exemptions, deviations and violations. Follow-up data will be reported for all participants, irrespective of random assignment, during the course of the study.

Study Stopping Rules. Formal stopping rules for safety, efficacy, and futility are not proposed given that this is a minimal risk clinical trial as the behavioral intervention to be tested are based on prior research in different populations without major harms (e.g., mortality or serious medical complications). Second, while we hypothesize that the intervention will lead to significant and clinically meaningful improvements in weight loss and other outcomes of interest, we expect the probability of major health benefits (e.g., reduced incidence of disease or reduced mortality) that would trigger early stopping for efficacy to be negligible over a 24-month follow-up period.

20.0 Provisions to Protect the Privacy Interests of Subjects

21.0 Compensation for Research-Related Injury

There are no plans for the study to provide free medical care or to pay for research-related illnesses or injuries, or to provide other forms of compensation (such as lost wages or pain and suffering) to participant for research related illnesses or injuries. As part of the informed consent process participants are advised to contact the site PI to report any illness or injury experienced from taking part in the Sustain study.

22.0 Economic Burden to Subjects

There are no costs to participants for intervention.

23.0 Consent Process

Multi-Stage Informed Consent. All study participants involved in the Sustain study must provide written informed consent before baseline assessment. Study personnel obtaining informed consent are experienced in obtaining informed consent and have receive standardized training in trial-specific protocols as well as mandatory trainings in good clinical research practice. For Sustain, there will be an

Reducing cardiometabolic risk and promoting functional health in community-based elders with obesity and pre-diabetes: evaluating sustainable follow-up strategies

initial screening consent (verbal authorization for phone or field screening) and subsequently written informed consent. We allow sufficient time and resources to meet the ethical obligations to research participants and to foster a progressively increasing understanding of the research as well as the development of rapport between subjects and research staff.

Informed Consent Process Training. We will conduct effective and efficient informed consent to ensure that participants understand the following: (1) that the study is for research purposes and in no circumstances does it supplant medical care provided by their health care provider(s), (2) the risks and benefits of the study, (3) the available alternatives, and (4) that their voluntary decision to participate or to not participant in this research will be accepted without penalty (i.e. without jeopardizing their medical care or relationship with their clinical sites). In reaching a decision about participation, it is essential for the potential subject to demonstrate an ability to use this information in a rational manner. Thus, in considering the risks, benefits, and available alternatives, subjects must show that they understand the aspects of these factors that are unique to them as individuals.

References

2. Group LAR. Eight-year weight losses with an intensive lifestyle intervention: the look AHEAD study. *Obesity (Silver Spring, Md)*. 2014;22(1):5.
